To estimate the prevalence of hepatitis C antibodies through rapid test screening and identify the behaviors associated with infection in people between 18 and 65 years of age who inject drugs in the city of Armenia.

Specific objectives

- Estimate the size of the population of people who inject drugs in the city of Armenia.
- Estimate the prevalence of antibodies against HCV in PWID.
- Socio-demographically characterize the study population.
- Describe the epidemiological characteristics of PWID with positive antibodies for HCV.
- Identify behaviors associated with HCV infection among PWID.
- Determine the proportion of PWID with positive HCV antibodies and positive HCV viral load.
- To carry out an exploratory analysis of the association of positive cases and the different risk factors for HCV infection among PWID.
- To quantify how many PWID with positive viral load for HCV were able to access the management route and treatment.

B. METHODOLOGICAL APPROACH

Type of study

An anonymous, confidential analytical cross-sectional study will be carried out, in which the prevalence of hepatitis C will be estimated, the behaviors associated with the consumption of psychoactive substances by injection will be analyzed in people between 18 and 65 years old who inject drugs in the city of Armenia.

Population and sample

Population

The universe for this study was people between 18 and 65 years old who have injected drugs in the last six months in Armenia and the participants were selected through the implementation of the respondent-driven sampling (RDS).

Inclusion and exclusion criteria

Inclusion criteria

- Be between 18 and 65 years old.
- Having injected psychoactive substances in the last six months.
- Residing in the city or metropolitan area of study in the last six months
- Present the invitation coupon.
- Person with Colombian nationality, Venezuelan migrant population.

Exclusion criteria

- Person who, due to physical, cognitive or limitations derived from the use of psychoactive substances, is not able to answer the survey autonomously.
- Person who is in a state of consumption and is prevented from responding to the survey.
- Person who refuses to collaborate in the study.

Sampling frame

Statistical units

The statistical units of analysis, observation and sampling are the key population of Armenia.

Target population size

Sample sizes and precision for estimating a population proportion.

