The RDS itself estimates the sampling errors described through measures such as homophily, heterophily, and proportional estimates of the population. Initially, homophily will be calculated, which describes the extent of the ties of the social network inside or outside it. The homophily/heterophily scale is between 1 and -1, where 1 indicates that all participants with certain characteristics invited someone with the same characteristics, while -1 indicates that all participants with a certain characteristic invite someone with one characteristic opposite or different; 0 (zero) was the point at which participants randomly invited other individuals from the population of all possible invitees.

The RDS technique uses the information available in the sample about the social network to obtain asymptotically unbiased estimators of the proportions of the population in the different groups in which they want to be characterized. These estimators are called population prevalence estimators.

Descriptive statistics (frequencies and percentages) will be estimated. For continuous quantitative variables, measures of central tendency (average and median) and measures of dispersion (variance, standard deviation) will be estimated.

A descriptive analysis of the characteristics of the population under study will be carried out, according to the socio-demographic variables: sex, age, educational level, stratum, insurance, in addition the prevalence of HCV and the proportions of the sample and the population will be obtained. according to the risk behavior variables associated with infections. All these analyzes are carried out by estimating the population with their corresponding 95% confidence intervals.

Possible relationships between sociodemographic variables, risk factors and documentation of positive antibodies for HCV will be explored. For this purpose, a bivariate analysis will be proposed using chi-square tests to explore the proposed associations. The test allows us to determine, for each pair of variables, the existence or not of the relationship through the difference between the value that should result if the two variables were totally independent, and the one observed in the data. The greater the difference, the greater the relationship between the variables.

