The significance between the relationships will be determined by the p-value of the test, a value less than 0.05, it is accepted that there is a statistical association between the two variables analyzed.

The processing will be carried out in the RDSAT® version 5.6 program.

C. WORK PLAN

Phase 1. Exploratory component

With the purpose of making an approach and identifying barriers to the study and possible alternative solutions to consumption contexts, as well as establishing inter-institutional alliances that facilitate communication with research subjects called seeds, an exploratory phase will be carried out through the use of a qualitative technique that enables the collection and construction of data that enriches the information obtained by the subsequent application of the structured survey that underpins the present study.

We will seek to identify characteristics of the social network: subgroups, connectivity, personal network, the acceptability of the study, interest, possible reasons for not

ID: CO-US-987-7106 - Version May 2024

participating, as well as define logistical aspects, such as the site for collecting information, schedules, coupon design and the profile of the personnel who will serve the prioritized populations.

Through interviews with representatives of various institutions in Armenia who, from research, care, and treatment, offer the research team a general overview of the context and care routes; and from there provide elements that guide field work and the analysis of the information obtained from the surveys.

After prioritizing institutions, they will be inquired about the description of the problem, characterization of the populations, institutional experiences, research, territorial location, methods of approach, risk behaviors and practices for HCV infection, among others. The estimated time to complete the exploratory phase will be two months, this includes the collection, analysis and interpretation of the data and the understanding of the conditions found.

Interviews with key informants

These people are considered experts in the social and cultural context of PWIDs, with the objective of understanding the context and behavior of users; example of key informants: people who have worked with populations, people from institutions, NGOs, among others. In this first phase, the capture technique, already described previously, will also be applied.

Phase 2. Quantitative component

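### The data analysis plan describes the chi-square difference as the strength of a relationship and the test as settling whether one exists; neither reading is sound across behaviours, and no effect estimate for the contrast is named

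*Protocol*

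**What the plan says.** Under section B, Data analysis plan, the protocol states that "a bivariate analysis will be proposed using chi-square tests to explore the proposed associations". It then explains how to read the test:

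- "The test allows us to determine, for each pair of variables, the existence or not of the relationship", by comparing what is observed with what independence would predict.
- "The greater the difference, the greater the relationship between the variables".
- On the p-value: "a value less than 0.05, it is accepted that there is a statistical association between the two variables analyzed".

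No odds ratio, prevalence ratio, prevalence difference or other measure of association is named. The same section does plan descriptive estimates of HCV prevalence and of proportions for the risk-behaviour variables, and says of them: "All these analyzes are carried out by estimating the population with their corresponding 95% confidence intervals". Those intervals are attached to population proportions. None is stated for the contrast between exposed and unexposed people.

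Under Objectives, identifying behaviours associated with infection is part of the general objective. It is repeated as a specific objective, "Identify behaviors associated with HCV infection among PWID", beside a further one worded "To carry out an exploratory analysis of the association of positive cases and the different risk factors for HCV infection among PWID".

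**The concern.** Both explanatory sentences are wrong as general statements about the test.

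- **Strength.** The departure from independence, and the chi-square built from it, combines the size of the effect with the sample size, the share exposed and the number of categories. A larger value for one behaviour than for another need not mean a stronger relationship.
- **Absence.** A test of independence can give evidence against independence. Failing to reject does not show that no relationship exists, least of all in a sample sized for something else.

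This is more than detail left to a statistical analysis plan. The protocol states an interpretive rule, and a later document that added an effect measure would have to contradict it. At stake is the behavioural half of the general objective: a common, weaker behaviour could be described as more strongly related than a rarer, stronger one, and a real association could be read as none.

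**Working it through.** **Inputs from the protocol.** Under Target population size: N = 580, assumed prevalence 77.8%, precision ±5 points, design effect 1, and n = 186 at 95% confidence, with a final sample of 205. From the problem statement: 69.6% antibody prevalence in Armenia in 2021. Effect sizes and exposure shares for behaviours are not given, so those below are assumptions.

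**The plan's own figure.** Np(1−p) / [(d²/z²)(N−1) + p(1−p)] with N = 580, p = 0.778, d = 0.05, z = 1.96 gives 182.3, so 183 against the stated 186 (within 3%). 186 × 1.10 = 204.6, which matches 205. The calculation serves prevalence precision only; no figure is given for the association tests.

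**Antibody-negative people.** 205 × (1 − 0.778) = 45.5 and 205 × (1 − 0.696) = 62.3, so about 45 to 62.

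**Does a greater difference mean a greater relationship?** For a two-by-two table with exposed share w, prevalences p1 and p0 and overall prevalence p:

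- observed minus expected, in the exposed-positive cell: n·w(1−w)(p1−p0)
- chi-square: n·w(1−w)(p1−p0)² / [p(1−p)]

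Both contain w(1−w), so both shrink as a behaviour becomes rarer. Two illustrative tables, each with 205 people and 160 positive (78%):

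| | Rarer behaviour | Common behaviour |
|---|---|---|
| Positive, exposed vs unexposed | 28/30 vs 132/175 | 85/100 vs 75/105 |
| Prevalence | 93.3% vs 75.4% | 85.0% vs 71.4% |
| Prevalence difference | 17.9 points | 13.6 points |
| Prevalence ratio | 1.24 | 1.19 |
| Odds ratio | 4.6 | 2.3 |
| Observed minus expected | 28 − 23.4 = 4.6 | 85 − 78.0 = 7.0 |
| Chi-square (p) | 4.79 (0.029) | 5.51 (0.019) |

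Every effect measure puts the rarer behaviour first; the protocol's difference and the chi-square put it second. The smallest expected cell is 30 × 45/205 = 6.6, so the test itself is usable here. The 95% intervals for the difference, from the standard error √[p1(1−p1)/n1 + p0(1−p0)/n0], are 17.9 ± 1.96 × 5.6 (about 7 to 29 points) and 13.6 ± 1.96 × 5.7 (about 2 to 25 points). They overlap widely, which the chi-square values do not convey.

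**Number of categories.** A chi-square of 8 gives p = 0.005 on 1 degree of freedom and p = 0.092 on 4. The planned variables include educational level and stratum, which would normally have several levels, beside sex.

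**Does non-significance show absence?** Power of the Pearson test at n = 205, overall prevalence 77.8%, two-sided 0.05, simple random sampling, by simulation:

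| True difference | 10% exposed | 20% | 30% | 50% |
|---|---|---|---|---|
| 10 points | 13% | 27% | 36% | 42% |
| 15 points | 30% | 59% | 70% | 75% |

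Check of one cell (10 points, 50% exposed): the standard error is √[0.778 × 0.222 / (205 × 0.25)] = 0.058; 0.10/0.058 = 1.72; Φ(1.72 − 1.96) ≈ 41%, in agreement. Clustering from RDS would lower these: with an assumed design effect of 2, power for a true odds ratio of 2 at 50% exposed falls from 53% to 30%.

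**The case against.** The case on the other side has real force.

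- **Within one pair of variables the sentence is true.** With the margins fixed, observed minus expected rises with the prevalence difference, ratio and odds ratio alike, and the text does speak of each pair separately. For complete two-by-two tables of equal size, chi-square is n·φ², so it orders behaviours by φ, a genuine though margin-dependent measure. This stands. The rule fails only when it is carried across behaviours with different exposure shares, numbers of levels or missing data.
- **No ranking is planned.** A reader might infer that behaviours will be ranked wrongly. The protocol nowhere says it will rank them, so only the possibility is supported.
- **Only the positive direction of the p-value rule is written.** A reader might infer that real associations will be declared absent. The rule says what p<0.05 means and is silent on p>=0.05, and the work is called exploratory. The sentence on existence or non-existence invites that reading but is not a reporting rule.
- **Choice of measure and further output.** Naming the effect measure is commonly left to an analysis plan. Prevalences by behaviour with intervals may show magnitude, and Information processing mentions secondary analysis in other packages. This weakens any complaint about a missing measure taken alone. It does not repair the interpretive sentences, and no interval for a contrast is stated.
- **Illustrations are fragile.** Moving one person in the rarer group above, to 29/30 vs 131/175, raises its chi-square to 7.1 and restores the order. With a behaviour at 8% exposed the smallest expected cell is 16.4 × 0.222 = 3.6 and significance turns on about one person. The tables show that a reversal can happen, not how often it will.

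**Conclusion.** The point holds in limited form. The Data analysis plan misdescribes the chi-square test in two sentences, and that test with p<0.05 is the only association analysis stated. Across behaviours that differ in exposure share or number of categories, the statistic can reverse the order given by the prevalence ratio, odds ratio and prevalence difference. A non-significant result will often be inconclusive: power is roughly 13-42% for a true 10-point difference and 30-75% for 15 points.

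These figures rest on n = 205, 77.8% prevalence, simple random sampling, and assumed effects with 10-50% exposed. The documents support misreading as a risk, not as a certain outcome. The prevalence estimate is not affected.

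**What to change.** In the Data analysis plan:

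1. Delete or correct the two interpretive sentences, on the size of the difference and on the existence or not of a relationship.
2. Report each association as an effect estimate with a 95% confidence interval that reflects the RDS weighting and design. A prevalence ratio or prevalence difference is preferable at this high prevalence, though the choice is partly one of preference. If an odds ratio is used, say that it is not a ratio of prevalences; in the common-behaviour table an odds ratio of 2.3 goes with a prevalence ratio of 1.19.
3. State that strength is judged from that estimate and its interval.
4. State that p>=0.05 is inconclusive and does not show absence.

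The cost is a few sentences and one extra column in the output tables. No new data are needed.

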of interest and who know a measurable number of people in that population. The seed is contacted, invited to the headquarters, the survey and the defined biological samples are applied, and they are given the three coded coupons that also contain the information about the study, the headquarters, and the opening hours. Each seed will deliver the coupons to known people who meet the eligibility criteria. Once the seeds have delivered their coupons to their peers, they are expected to come to the headquarters to participate, once the information collection process is completed. In this way, the enrollment process is developed in waves until the predefined sample size is reached. Each coupon contains information about the headquarters, including the address, opening hours and contact telephone number, as well as the RDS code assigned to each participant, which allows identifying who recruited whom and reconstructing the chain of referrals or recruitment.

Potential participants will be presented with the purposes of the research, and it will be asked if they are interested in participating. The informed consent will be read and explained to them, and they will subsequently be asked to sign the consent. The standardized information collection phase will then proceed. These individuals will undergo pre-test counseling, a presumptive rapid test for HCV, and if positive, contact information will be requested for post-test counseling.

The collection of information on social and demographic variables, risk factors associated with HCV infection, and access to the health system will be carried out with the application of a structured survey conducted by a previously trained interviewer. You will explore social and demographic characteristics, social networks, drug use and injection, sexual behavior, sexually transmitted infections, HCV knowledge, and rapid test results and viral load.

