Each of the participants is asked about the number of acquaintances, the coupon system limits the possibility for each informant to select only three future informants, to nullify the biases caused by the presence of semi-professional recruiters or by a desire for super-collaboration by some people that would cause an overrepresentation of the networks of a specific individual.

Instructions for recruitment

- They must bring their coupons with them to the site, if the referral does not bring their coupon, they cannot participate in the survey.
- Coupons are limited, it is recommended to give the coupons to people you know who meet the criteria as soon as possible.
- One hour and 30 minutes are required to complete the interview and sample collection.
- Those referred will receive a social support bonus if they complete the interview and sample collection.
- Referrals who are not eligible (not meeting inclusion criteria), participants who do not sign the informed consent, who had already participated and if the person sells their coupons are not considered (only the social support voucher will be given to the person to whom which they were delivered).

Social network

They will be consulted about the following aspects corresponding to the social network, having the protocol it is expected to have at least the following information:

- How many people do you know (you know them, and they know you)?
- Of them, how many are over 18 years old?
- And of them, how many have you seen in the last month?
- Each person receives three (3) coupons to recruit others.
- The study will end when the required sample size is met.
- A day is scheduled to deliver the social support vouchers.

Delivery of social support bonuses

- Reiterate the recruitment process to the participant.
- Deliver the primary social support bonus.
- Confirm to the participant that they have completed all steps of the study (otherwise have the participant complete them).
- They must bring the coupons, in the part of the detachable assigned for the participants.
- It is investigated whether some people rejected the coupons and the reasons for this situation.
- It is consulted for doubts or questions that the participants have.
- Verify that the recruit is enrolled in the study. Inform the recruiter to return if the previous coupon was not registered.

Other activities

- Ensure the quality of the numbers on the coupons.
- Update the coupon registration form.

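### The listed network-size questions count all acquaintances, not people who inject drugs, so the RDS degree would not match the network in which coupons can be passed

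*Protocol*

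**What the plan says.** In section C, Phase 2, the Coupons text states that "Each of the participants is asked about the number of acquaintances". The Social network list that follows is a minimum: "it is expected to have at least the following information". Its three nested items are:

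1. "How many people do you know (you know them, and they know you"
2. "Of them, how many are over 18 years old"
3. "And of them, how many have you seen in the last month"

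The Coupon Registration list then requires the participant's network size to be recorded, without defining it.

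The rules on who may receive a coupon are narrower. Under Instructions for recruitment, "it is recommended to give the coupons to people you know who meet the criteria as soon as possible". For seeds, section B (Collection of information and sampling procedure) says "Each seed will deliver the coupons to known people who meet the eligibility criteria". The Inclusion criteria are age 18 to 65, injecting in the last six months, residence in the city or metropolitan area in the last six months, a coupon, and a nationality or migrant criterion.

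Sample design (section B) says that numbers of social contacts are tracked and that a recruitment model weights the sample. The Data analysis plan bases the population prevalence estimators on network information in the sample.

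**The concern.** In RDS, a participant's degree stands in for the chance of being recruited. It should therefore count the people with whom a coupon could be exchanged, here eligible people who inject drugs. The listed items count everyone the participant knows. They carry over the lower age limit but not the criterion that defines the population, nor residence.

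This is a data-collection matter. If the number of injecting contacts is never asked, no analysis plan can reconstruct it. The weighted results, including the main prevalence estimate, would rest on a degree from a different network. A larger sample would not remove any bias that results.

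**Working it through.** **Comparison of the text**

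| Criterion | Who may get a coupon | Listed network items |
|---|---|---|
| Injected in last six months | required | absent |
| Resident in study area, last six months | required | absent |
| Age | 18 to 65 | over 18, no upper limit |
| Known to the recruiter | required | yes, mutual |
| Seen in last month | not stated | yes |

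Read literally, over 18 also leaves out eligible 18-year-olds. The right reference group appears once, in Collection of information and sampling procedure, where seeds are people "who know a measurable number of people in that population". That is a criterion for choosing seeds, not a question put to participants.

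**The plan's own figures.** The protocol gives no figure for network size. Its sample size does not depend on these items. With N = 580, p = 0.778, d = 0.05 and design effect 1, the stated formula gives 182.3, so 183, against the stated 186; and 186 × 1.10 = 204.6, so 205. Rewording the network items changes none of this.

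**Effect on the weighted estimate**

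Let each participant's counted contacts be k times their eligible injecting contacts. Let c be the typical k in HCV-positives divided by that in HCV-negatives. The weights are reciprocals of degree, so the relevant average of k within each group is a harmonic mean.

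- Inverse-degree weighting divides the weighted odds of being positive by c. If the correct degree would give p, the estimate becomes p / (p + c(1 − p)).
- The form based on mean degrees and cross-recruitment proportions gives the same: multiplying the ratio of mean degrees by c again divides the odds by c.
- With c = 1 the inflation cancels. Unweighted proportions are unaffected for any c.

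Inputs: p = 77.8%, its ±5 range (72.8% and 82.8%) and d = 5 points come from Target population size. The 69.6% is the Armenia 2021 figure in Problem statement and justification. **c is an assumption; the protocol gives no value.**

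At p = 0.778:

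- c = 0.9: 0.778 / (0.778 + 0.9 × 0.222) = 0.778 / 0.9778 = 79.6%, or +1.8 points
- c = 1.1: 0.778 / (0.778 + 1.1 × 0.222) = 0.778 / 1.0222 = 76.1%, or −1.7 points
- c = 0.8 and 1.25: 81.4% and 73.7%, or +3.6 and −4.1 points
- c = 0.5 and 2: 87.5% and 63.7%

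The c at which the bias equals 5 points is p(1 − q) / (q(1 − p)), with q = p ± 0.05. At p = 0.778:

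- upward, q = 0.828: (0.778 × 0.172) / (0.828 × 0.222) = 0.728
- downward, q = 0.728: (0.778 × 0.272) / (0.728 × 0.222) = 1.309

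| p | Bias at c = 0.9 | Bias at c = 1.1 | c for +5 points | c for −5 points |
|---|---|---|---|---|
| 69.6% | +2.18 | −2.05 | 0.780 | 1.255 |
| 72.8% | +2.04 | −1.93 | 0.764 | 1.271 |
| 77.8% | +1.77 | −1.69 | 0.728 | 1.309 |
| 82.8% | +1.45 | −1.40 | 0.669 | 1.374 |

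**The case against.** The list is only a minimum, and the questionnaire is not in the document. Quality assurance procedure says the instrument was used and reviewed in earlier research. Pilot test and Field work provide for adjusting it. The survey may well restrict the count already. The English reads as a translation, and the list follows closely on the instruction about eligible peers, so people may have been meant as people who inject drugs. The screening questionnaire (Procedure for selecting possible seeds) also asks about other people who might be eligible. Finally, the size of any bias depends entirely on the chosen c.

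Much of this stands: the defect is conditional, and bias has not been demonstrated. But nothing in the protocol supplies the restriction for the network-size question, and the screening text is not a degree item. A minimum list should contain the item the estimator needs. Interviewers are told to ask questions exactly as worded, so they cannot be relied on to add an unstated restriction. If the restriction was intended, writing it down settles the point.

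A further objection is that equal arithmetic mean ratios do not guarantee zero bias. If HCV-negatives all have k = 10 and positives are split evenly between 5 and 15, the mean of 1/k is 0.100 against 0.133. Then c is 0.75, and 77.8% becomes 82.4%. That is correct, and is why c is defined through harmonic means above. It is still a difference in the ratios by HCV status, so it refines the condition without removing it.

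**Conclusion.** The concern holds and should be fixed before fieldwork. The mismatch between the listed items and the coupon rules is plain from the text. Its effect on the estimates is conditional: the survey must follow the list, and the ratio of counted to eligible contacts must differ by HCV status. The protocol informs neither condition, so size and direction are unknown.

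Over the protocol's own values of p, a 10% difference in the ratio moves weighted prevalence by about 1.4 to 2.2 points. Reaching the planned 5-point precision takes a ratio 22% to 33% lower, or 25% to 37% higher, in HCV-positives than in HCV-negatives. These figures illustrate an assumed c and do not estimate the bias.

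**What to change.** At the instrument review and pilot already planned, replace the three items with:

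1. How many people do you know, who also know you, who have injected drugs in the last six months and have lived in Armenia or its metropolitan area over that time?
2. Of these, how many are aged 18 to 65?
3. Of these, how many have you seen in the last month?

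State which count is the network size entered at coupon registration and used as the degree in the weights; the third is the natural choice. If the earlier instrument's item must stay for comparability with previous surveys, keep it and add the restricted items beside it. If the survey already restricts the count, align the protocol's list with it.

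The cost is rewording, or one or two extra questions in a survey of about 60 minutes. No extra participants or staff are needed, and the sample size does not change.
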